#### Using shells 14.3.3.2.1 and 14.3.3.2.2, repeat for the following:

Table 14.3.3.3.1 Treatment-Related Emergent Adverse Events by System Organ Class, Preferred Term, and Duration of Exposure Safety Population

Table 14.3.3.3.2 Treatment-Related Emergent Adverse Events by System Organ Class, Preferred Term, and Extent of Exposure Safety Population

Programmer's Note: subset on TEAEs related to study treatment.

Table 14.3.3.4.1 Treatment Emergent Adverse Events Leading to Treatment Modification by Duration of Exposure Safety Population

Table 14.3.3.4.2 Treatment Emergent Adverse Events Leading to Treatment Modification by Extent of Exposure Safety Population

Programmer's Note: subset on TEAEs leading to treatment modification. Add the following footnote:

Note: Treatment modification includes reduction, interruption, or discontinuation of Study Drug

Table 14.3.3.5.1 Treatment-Related Treatment Emergent Adverse Events Leading to Treatment Modification by Duration of Exposure Safety Population

Table 14.3.3.5.2 Treatment-Related Treatment Emergent Adverse Events Leading to Treatment Modification by Extent of Exposure Safety Population

Programmer's Note: subset on Treatment-Related TEAEs leading to treatment modification. Add the following footnote:

Note: Treatment modification includes reduction, interruption, or discontinuation of Study Drug.

Table 14.3.3.6.1 Treatment Emergent Adverse Events Leading to Discontinuation of Study Drug by Duration of Exposure Safety Population

Table 14.3.3.6.2 Treatment Emergent Adverse Events Leading to Discontinuation of Study Drug by Extent of Exposure Safety Population

Programmer's Note: subset on TEAEs leading to discontinuation of Study Drug.

Table 14.3.3.7.1 Treatment-Related Treatment Emergent Adverse Events Leading to Discontinuation of Study Drug by Duration of Exposure Safety Population

Protocol Number: NI-AC303

Table 14.3.3.7.2 Treatment-Related Treatment Emergent Adverse Events Leading to Discontinuation of Study Drug by Extent of Exposure Safety Population

Programmer's Note: subset on Treatment-Related TEAEs leading to discontinuation of Study Drug.

Table 14.3.3.8.1 Treatment Emergent Serious Adverse Events by System Organ Class, Preferred Term, and Duration of Exposure Safety Population

Table 14.3.3.8.2 Treatment Emergent Serious Adverse Events by System Organ Class, Preferred Term, and Extent of Exposure Safety Population

Programmer's Note: subset on Serious TEAEs.

Table 14.3.3.9.1 Treatment-Related Treatment Emergent Serious Adverse Events by System Organ Class, Preferred Term, and Duration of Exposure Safety Population

Table 14.3.3.9.2 Treatment-Related Treatment Emergent Serious Adverse Events by System Organ Class, Preferred Term, and Extent of Exposure Safety Population

Programmer's Note: subset on Treatment-Related Serious TEAEs.

Table 14.3.3.10.1 Treatment Emergent Adverse Events Leading to Death by Duration of Exposure Safety Population Table 14.3.3.10.2 Treatment Emergent Adverse Events Leading to Death by Extent of Exposure Safety Population

Programmer's Note: subset on TEAEs with fatal outcome.

Table 14.3.3.11.1 Treatment-Related Treatment Emergent Adverse Events Leading to Death by Duration of Exposure Safety Population

Table 14.3.3.11.2 Treatment-Related Treatment Emergent Adverse Events Leading to Death by Extent of Exposure Safety Population

Programmer's Note: subset on treatment related TEAEs with fatal outcome.

•

Protocol Number: NI-AC303

Table 14.3.3.13

Summary of Treatment Emergent Adverse Events (TEAE) by Highest Severity, System Organ Class and Preferred Term Safety Population

System Organ Class		SB204
Preferred Term	Severity	(N=XXX)
Subjects with at least one event	Mild	xx (xx.x)
	Moderate	xx (xx.x)
	Severe	xx (xx.x)
Number of events	Mild	XX
	Moderate	XX
	Severe	XX
System Organ Class 1	Mild	xx (xx.x)
	Moderate	xx (xx.x)
	Severe	xx (xx.x)
Preferred Term 1	Mild	xx (xx.x)
	Moderate	xx (xx.x)
	Severe	xx (xx.x)

Note(s): TEAE onset is based on the start of treatment in the LTS. Adverse event terms were coded using MedDRA dictionary version 18.1. Subjects are counted once within each level of summary. If a subject has multiple events, the event with highest severity will be considered.

Source: Listing xx.x.x.x, Program: xxxxx.sas, Output: T xx.x x x xxxx.rtf, Generated on: DDMMMYYYY HH:MM

Programmer Note: Order SOC by decreasing frequency and preferred term by decreasing frequency within SOC based on overall incidence.

Protocol Number: NI-AC303

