in this long-term safety study. Inclusion criteria: • Have no more than two nodules on the face; Completed 12 weeks of treatment in NI-AC301 or NI-AC302 Exclusion Criteria: Terminated early from an SB204 Phase 3 pivotal study for any reason; • Have any dermatological conditions on the face that could interfere with clinical evaluations such as acne conglobata, acne fulminans, acne secondary to medications or other medical conditions, perioral dermatitis, clinically significant rosacea, or gram-negative folliculitis; • Have an on-going adverse event at the Week 12 visit for NI-AC301 or NI-AC302 that warrants stopping study drug application; • Have facial hair, tattoos or other facial markings that would interfere with efficacy and safety assessments; • Have any underlying disease(s) or some other dermatological condition of the face that requires the use of interfering topical or systemic therapy or makes evaluations and lesion count inconclusive; • Have used medications or vitamins during the 12 weeks immediately preceding Baseline which are reported to exacerbate acne (e.g. azathioprine, haloperidol, halogens such as iodides or bromides, lithium, anabolic steroids, systemic corticosteroids, phenytoin and phenobarbital). Daily use of a multi-vitamin is acceptable. Approximately 600 subjects will be entered into the study. **Sample Size** Safety and tolerability assessments will be collected beginning at the Safety and Baseline visit for NI-AC303. The subject must enroll in NI-AC303 **Tolerability Evaluation** within 7 days of completion of NI-AC301 or NI-AC302. Demographics and the subject's Week 12 visit values from NI-AC301 or NI-AC302 for blood pressure, pulse, urine pregnancy test, physical exam findings, lesion counts and tolerability will be used as the Baseline values for NI-AC303. Adverse events will be assessed and collected at each evaluation beginning at Baseline. A brief physical exam will be collected at Week 40/Early Termination (ET). Blood pressure and pulse will be collected at each visit through Week 40/ET. Urine pregnancy tests in women of

	child-bearing potential (WOCBP) will be conducted at each visit.

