3.7.2 INCLUSION CRITERIA

Each subject must fulfill all of the following inclusion criteria to participate in the study:

- 1. Have a signed written informed consent form. Subjects less than 18 years of age or the age of majority in their state must sign an assent form for the study and a parent or a legal guardian must sign the informed consent;
- 2. Have completed the full 12 weeks of treatment in NI-AC301 or NI-AC302;
- 3. Be in good general health;
- 4. Have no more than two nodules or cysts on the face;
- 5. Women of childbearing potential (WOCBP) must have a negative urine pregnancy test (UPT) prior to enrollment;
- 6. WOCBP must agree to use an effective method of birth control during the course of the study and for 30 days after their final study visit;
- 7. Be willing and able to follow study instructions and likely to complete all study requirements. Subjects under 18 years of age or age of majority must be accompanied by the parent or legal guardian at the time of assent/consent signing.

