3.7.3 EXCLUSION CRITERIA

Subjects will not be enrolled if they meet any of the following exclusion criteria:

- 1. Have any dermatological conditions on the face that could interfere with clinical evaluations such as acne conglobata, acne fulminans, acne secondary to medications or other medical conditions, perioral dermatitis, clinically significant rosacea, or gram-negative folliculitis;
- 2. Have any underlying disease(s) or some other dermatological condition of the face that requires the use of interfering topical or systemic therapy or makes evaluations and lesion count inconclusive;
- 3. Have an on-going adverse event at the Week 12 visit for NI-AC301 or NI-AC302 that warrants stopping study drug application;
- 4. Are transgender persons who are taking testosterone (female to male) or estrogen (male to female);
- 5. Have facial hair, tattoos or other markings that could interfere with assessments or application of study drug;
- 6. Have a history of experiencing significant burning or stinging when applying any facial treatment (e.g., make-up, soap, masks, washes, sunscreens, etc.) to their face;
- 7. Female subjects who are pregnant, nursing mothers, or planning to become pregnant during the study;

- 8. Intend to use a tanning booth or sunbathe during the study;
- 9. Are members of the same household where a subject is enrolled in NI-AC301, NI-AC302, or NI-AC303;
- 10. Are immediate family members of study site personnel directly involved in NI-AC301, NI-AC302, or NI-AC303;
- 11. Have any condition or situation which, in the Investigator's opinion, puts the subject at significant risk, could confound the study results, or may interfere significantly with the subject's participation in the study;
- 12. Are unable to communicate or cooperate with the Investigator due to language problems, poor mental development, or impaired cerebral function;
- 13. Concurrently participating in a different interventional research study.

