# 3 Study Design

### 3.1 Study Design

This is a multi-center, open label long-term safety (LTS) study to be conducted in approximately 600 subjects with acne vulgaris. Subjects will be enrolled into the study from approximately 100

sites in North America. Subjects eligible to enroll in this study will have completed one of the Phase 3 pivotal studies with SB204, NI-AC301 or NI-AC302, and meet study inclusion and exclusion criteria.

Subjects who satisfy the entry criteria at the Baseline visit will be enrolled to receive open-label SB204. Investigational drug will be delivered from a double barrel single pump dispenser. The pump dispenses product (NVN1000 Gel and a hydrogel) from two chambers which will be mixed together quickly (about 5 seconds) by the subject and applied once daily to the acne affected areas identified by the Investigator. Areas that could be treated include the face, upper chest, upper back and shoulders. No other acne treatments will be permitted during the study.

Subjects will return for post-baseline evaluation at Weeks 4, 12, 24, 36 and 40/ET.

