#### 3.5 Populations

#### 3.5.1 Safety Population

The safety population (SAF) will include all subjects that have received at least one dose of SB204. For the summaries, we are defining two subject categories, based on the subject's status at the start of the LTS:

- SB204 Experienced: subjects allocated to SB204 in the previous study
- SB204 Naïve: subjects allocated to vehicle in the previous study

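### SOC/PT and severity TEAE tables do not separate SB204 Experienced from Naive subjects, which may mask early-onset events in first users and dilute signals that rise with cumulative exposure

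*SAP*

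**What the plan says.** SAP 3.5.1 sets up the grouping: "For the summaries, we are defining two subject categories, based on the subject's status at the start of the LTS". The first is "SB204 Experienced: subjects allocated to SB204 in the previous study"; the second is those allocated to vehicle.

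The mock tables use this split for demographics (14.1.2.1), ongoing adverse events by SOC and PT (14.1.4), exposure (14.2.1), lesion counts (14.2.3.1, 14.2.3.2) and the TEAE overview (14.3.3.1). The overview has no SOC, PT or severity rows. The table that does, "Summary of Treatment Emergent Adverse Events (TEAE) by Highest Severity, System Organ Class and Preferred Term Safety Population" (14.3.3.13), has one SB204 column, and 14.3.3.14 reuses its shell for related events.

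Three entry conditions shape both groups. Protocol 3.7.2 requires that subjects "Have completed the full 12 weeks of treatment in NI-AC301 or NI-AC302". The synopsis excludes a subject who "Terminated early from an SB204 Phase 3 pivotal study for any reason". Protocol 3.7.3 excludes those who "Have an on-going adverse event at the Week 12 visit for NI-AC301 or NI-AC302 that warrants stopping study drug application".

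SAP 4.3 and 4.5.1 add that adverse events still ongoing when the pivotal study ends are carried forward, are not treatment-emergent here, and are summarised separately.

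**The concern.** The two groups contribute different stretches of SB204 exposure. A Naive subject meets the drug for the first time in NI-AC303. An Experienced subject enters after finishing 12 weeks on it, with no ongoing event that warranted stopping. A reaction to SB204 that began in the pivotal study and persists is not a TEAE for the Experienced subject; the same reaction starting in NI-AC303 is one for the Naive subject.

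If an event comes early or leads people to stop, a pooled column may show a lower rate and milder severity than first users experience. If an event builds with cumulative exposure, pooling may dilute it with subjects who have less exposure. In either case the overview could show a difference between the groups that no planned table explains by term or severity. Safety is the primary objective, yet lesion counts are reported by prior treatment and term-level TEAEs are not.

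**Working it through.** The documents state no event rate, allocation ratio or power figure, so there is no figure of the plan's to reproduce. SAP 3.1 gives only the total: "conducted in approximately 600 subjects with acne vulgaris".

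**1. Columns of the TEAE displays**

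| Display | Columns | SOC/PT or severity? |
|---|---|---|
| 14.3.3.1 overview | Experienced, Naive, Overall | No |
| 14.3.3.2.1 to 14.3.3.11.2 | Duration windows or grams | SOC/PT in the shells |
| 14.3.3.13, 14.3.3.14 | One SB204 column | Both |
| Listing 16.2.8.1 | No prior-treatment column | Both, by subject |

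No SOC/PT or severity TEAE table is split by prior treatment.

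**2. Can the duration table stand in for the split?** The note under Table 14.3.3.2.1 counts duration from the first SB204 dose, which may lie in the pivotal study. Assume 84 pivotal days, no gap at entry and 280 days in NI-AC303. Naive subjects then cover days 1 to 280, and Experienced subjects days 85 to 364.

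| Window (days) | Naive days | Experienced days |
|---|---|---|
| 1 | 1 | 0 |
| 2–30 | 29 | 0 |
| 31–90 | 60 | 6 |
| 91–180 | 90 | 90 |
| 181–365 | 100 | 184 |

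On this clock the first two columns hold Naive events only. But SAP 4.5.1 puts the first window at Day 1 of the long-term study, which mixes the groups from the start. The column N is also undefined. If it is the whole safety population, a true 5% Naive rate in an early window prints as 5% × (1 − w), where w is the Experienced share: 3.3%, 2.5% or 1.7% for an assumed w of 1/3, 1/2 or 2/3. Neither clock helps with severity.

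**3. Effect of pooling on one term.** Pooled rate = w·pE + (1 − w)·pN. With an assumed Naive rate pN = 10%:

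| pE/pN | w = 1/3 | w = 1/2 | w = 2/3 |
|---|---|---|---|
| 0.25 | 7.5% | 6.25% | 5.0% |
| 0.5 | 8.3% | 7.5% | 6.7% |
| 1.0 | 10.0% | 10.0% | 10.0% |
| 1.25 | 10.8% | 11.25% | 11.7% |

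For example, at ratio 0.5 and w = 1/2: 0.5 × 5% + 0.5 × 10% = 7.5%.

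**4. Direction depends on when risk falls.** Let the risk be a over the first 84 days on SB204 and b per 84 days afterwards. Over 280 study days, Naive risk = 1 − (1 − a)(1 − b)^(196/84) and Experienced risk = 1 − (1 − b)^(280/84). Assuming equal group sizes:

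| Assumed pattern | Naive | Experienced | Pooled |
|---|---|---|---|
| Early (a = 10%, b = 5%) | 20.2% | 15.7% | 17.9% |
| Constant (a = b = 10%) | 29.6% | 29.6% | 29.6% |
| Late (a = 5%, b = 10%) | 25.7% | 29.6% | 27.7% |

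Pooling lowers the first-user figure in the first row, changes nothing in the second, and in the third dilutes the signal seen with longer exposure.

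**The case against.** A reader might infer that pooled rates must understate new-user risk. The documents do not support that. It holds only if the Experienced rate is below the Naive rate; no rates are given, and the direction reverses for late-rising events.

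Several other points also stand.

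- Protocol 4.2 keeps tolerability findings out of adverse event reporting unless they are severe or lead to discontinuation. Mild or moderate erythema, scaling, dryness, pruritus and burning or stinging, the obvious early events, therefore mostly appear in Tables 14.3.1.x and 14.3.2.x.
- The overview already gives any, related, treatment-modifying, treatment-ending, serious and fatal TEAEs by group. Carried-over events appear by group in Table 14.1.4.
- Listing 16.2.1.1 shows the previous treatment group by subject, so individual events can be traced by hand.
- The entry filter is narrower than selection for never having had an event that stopped drug. It concerns an event ongoing at Week 12, so a resolved event with a temporary interruption does not exclude. According to SAP 4.4, pivotal dosing was to the face only, so Experienced subjects are not selected for tolerance on other areas.
- Protocol 7.5.1 asks for exposure windows and extent of exposure, not prior-treatment columns, and the wording of SAP 3.5.1 does not promise the split in every summary.

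The early columns of Table 14.3.3.2.1 are the best counter-argument, but they help only if the shell-note clock applies and N is the number at risk. The SAP settles neither, and severity is left uncovered.

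**Conclusion.** The omission is real and worth correcting, as an inexpensive improvement to the displays. The pooled columns of Tables 14.3.3.13 and 14.3.3.14 may understate first-user rates and severity for early-onset or treatment-limiting events, and may dilute a signal that grows with cumulative exposure. The size cannot be stated. The illustrations rest on assumed rates, an assumed Experienced share of one-third to two-thirds and assumed timing of risk; they show the mechanism and do not predict results.

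It would be tempting to read the Naive column as the estimate for new users. That goes too far: Naive subjects are themselves selected as people who completed 12 weeks on vehicle, and Protocol 1.5 says that local reactions may come from the vehicle as well as the active agent.

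**What to change.** - Give Tables 14.3.3.13 and 14.3.3.14 the columns SB204 Experienced, SB204 Naive and Overall, each on its own N, with total rows for each SOC and PT.
- Add prior treatment to Listing 16.2.8.1.
- Choose one exposure clock for Table 14.3.3.2.1 and the tables that reuse its shell, reconciling SAP 4.5.1 (Day 1 of the long-term study) with the shell note (first SB204 dose), and define each column's N as the subjects at risk in that window.
- Add a footnote that the Experienced column is conditional on completing 12 weeks of SB204 and the Naive column on completing 12 weeks of vehicle. Do not label the Naive column as the new-user estimate.

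The grouping variable already exists and no new data are needed. The cost is SAP and shell wording, the programming of an at-risk N, and wider tables.

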#### Using shell 14.3.3.13, repeat table for the following:

Table 14.3.3.14 Summary of Treatment-Related Emergent Adverse Events (TEAE) by Severity, System Organ Class and Preferred Term Safety Population

Programmer's Note: subset on related TEAEs

Protocol Number: NI-AC303

Table 14.3.4
Summary of Vital Signs
Safety Population

#### <Parameter> (<units>)

	-	SB204
		N=XXX)
Timepoint	Actual	Change from Baseline
Baseline		
n	XX	
Mean (SD)	xx.x (xx.xx)	
Median	XX.X	
Min, Max	XX, XX	
Missing	xx	
Week 4		
N	XX	XX
Mean (SD)	xx.x (xx.xx)	xx.x (xx.xx)
Median	XX.X	XX.X
Min, Max	xx, xx	XX, XX
Missing	xx	XX
Week 12		
n	XX	XX
Mean (SD)	xx.x (xx.xx)	xx.x (xx.xx)
Median	XX.X	XX.X
Min, Max	xx, xx	xx, xx
• • • •		XX

Note(s): Baseline is defined as the Week 12 assessment from the previous study (NI-AC301 or NI-AC302). Source: Listing xx.x.x.x, Program: xxxxx.sas, Output: T\_xx.x\_x\_x\_xxxx.rtf, Generated on: DDMMMYYYY HH:MM

Programmer Note: Include all vital signs parameters (e.g. SBP, DBP, Pulse) and all available post-baseline visits. Missing not presented if no missing values.

#### **Protocol: NI-AC303**

A Phase 3 Multi-Center, Open Label Study Evaluating the Long Term Safety of SB204 Once Daily in the Treatment of Acne Vulgaris.

Mock Data Displays - Figures Version 1.0 Date: 12Apr2017

> Prepared for: Novan Inc. [name]

Prepared by:
Chiltern International
[name]

[figure not shown]
This document is the confidential information of Novan Inc. It may not be disclosed to parties not associated with the clinical investigation or used for any purpose without the prior written consent of Novan Inc.

Contents

Figure 14.1.1 Distribution of Erythema Scores by Treatment and Visit Safety Population
Figure 14.1.2 Distribution of Dryness Scores by Treatment and Visit, Safety Population
Figure 14.1.3 Distribution of Scaling Scores by Treatment and Visit, Safety Population
Figure 14.1.4 Distribution of Pruritus Scores by Treatment and Visit, Safety Population
Figure 14.1.5 Distribution of Burning/stinging Scores by Treatment and Visit, Safety Population
Figure 14.2.1 Average Change from Baseline in Inflammatory Lesion Count Over Time Safety Population
Figure 14.2.2 Average Percent Change from Baseline in Inflammatory Lesion Count Over Time Safety Population 6
Figure 14.3.1 Average Change from Baseline in Non-Inflammatory Lesion Count Over Time, Safety Population7
Figure 14.3.2 Average Percent Change from Baseline in Non-Inflammatory Lesion Count Over Time, Safety Population 7

Figure 14.1.1 Distribution of Erythema Scores by Treatment and Visit Safety Population

Figure 14.1.1
Distribution of Erythema Scores by Treatment and Visit
Safety Population

Using shell for Figure 14.1.1, repeat for the following:

Figure 14.1.2 Distribution of Dryness Scores by Treatment and Visit, Safety Population

Figure 14.1.3 Distribution of Scaling Scores by Treatment and Visit, Safety Population

Figure 14.1.4 Distribution of Pruritus Scores by Treatment and Visit, Safety Population

Figure 14.1.5 Distribution of Burning/stinging Scores by Treatment and Visit, Safety Population

Figure 14.2.1 Average Change from Baseline in Inflammatory Lesion Count (Face only) Over Time Safety Population

 $\begin{tabular}{lll} Figure 14.2.1 \\ Average Change from Baseline in Inflammatory Lesion Count Over Time \\ Safety Population \\ \end{tabular}$ 

[figure not shown]
[figure not shown]

Figure 14.2.2 Average Percent Change from Baseline in Inflammatory Lesion Count (Face only) Over Time
Safety Population

Figure 14.2.2

Average Percent Change from Baseline in Inflammatory Lesion Count Over Time
Safety Population

Using shell for Figure 14.2.1, repeat for the following:

Figure 14.3.1 Average Change from Baseline in Non-Inflammatory Lesion Count (Face only) Over Time, Safety Population

Using shell for Figure 14.2.2 repeat for the following:

Figure 14.3.2 Average Percent Change from Baseline in Non-Inflammatory Lesion Count (Face only) Over Time, Safety Population

### Listing 16.2.2 Protocol Violations/Deviations Safety Population

Subject ID	Date of Violation/ Deviation /Day	Type of Violation	Details of Violation/Deviation
xxxxxx	DDMMMYYYY/xx	ICF Issue	xxxxxxxxxxxxxxxxxxxxxxxxxxxxxxxxxxxxxxx
xxxxxxx	DDMMMYYYY/xx	Assessment not Performed per Protocol	xxxxxxxxxxxxxxxxxxxxxxxxxxxxxxxxxxxxxxx
xxxxxxx	DDMMMYYYY/xx	Non-compliance with IP	xxxxxxxxxxxxxxxxxxxxxxxxxxxxxxxxxxxxxxx

Note(s): Day = Day relative to the date of first dose of study medication. s<nnn>xxxx yyyymmddthh:mm

Programmer's Note(s): This and subsequent listings will be sorted by Subject ID.

Protocol Number: NI-AC303

